# **PROTOCOL SYNOPSIS**

TITLE:	A phase IIa, single-blind, placebo-controlled, crossover, multi-center, randomized study to assess the safety, tolerability, and preliminary efficacy of a single intravenous dose of ischemia-tolerant allogeneic mesenchymal bone marrow cells to subjects with heart failure of non-ischemic etiology
PROTOCOL NUMBER:	STEM-104-M-CHF
INVESTIGATIONAL PRODUCTS:	Ischemia-Tolerant Allogeneic Mesenchymal Bone Marrow Cells (aMBMC), (adult human)
PHASE:	lla
INDICATION:	Heart failure of non-ischemic etiology
IND/IDE NUMBER:	
SPONSOR:	CardioCell, LLC

## STUDY OBJECTIVES

#### Primary:

To assess the safety of human ischemia-tolerant allogeneic mesenchymal bone marrow cells (aMBMC) administered intravenously to subjects with heart failure (HF) of non-ischemic etiology (N-IHF).

#### Secondary:

To assess the effects of intravenously delivered human aMBMC on (a) left ventricular (LV) structure and function, and (b) clinical status of subjects with N-IHF.

#### **STUDY DESIGN**

This is a Phase IIa, single blind, placebo-controlled, crossover, multi-center, randomized study in subjects with NIHF. The study will enroll 20 subjects and will consist of 2 cohorts. Enrolled subjects will be randomized at 1:1 into an experimental group (n=10) or a placebo group (n=10), respectively. Subjects in the experimental group will receive 1.5 million cells per kg and subjects in the placebo group will receive 1 mL/kg Lactated Ringer's Solution. At 90 days the two groups will change arms and the placebo group will receive 1.5 million cells per kg and the initially treated group will receive a Lactated Ringer's Solution (LRS) at a volume of 1 mL/kg.

#### SUBJECT PARTICIPATION

To be eligible for screening, participants must be diagnosed with N-IHF with previous angiographically or cardiac CTA documented no or non-significant coronary artery disease (less than 30% left main or <50% stenosis of any other major coronary artery and no clinical history of myocardial infarction). The screening evaluation will include obtaining written informed consent, collection of a complete medical history, including current and past medications, physical examination and laboratory tests. A quantitative echocardiogram  $\leq$ 6 months prior to evaluation is also required for assessment of LV function. If the subject's LV ejection fraction (LVEF) is  $\leq$ 40% determined by echocardiography in the past twelve months, the patient will be eligible for screening for the study.

A baseline cardiac magnetic resonance imaging (MRI) scan will be obtained with delayed contrast enhancement to measure cardiac structure and function prior to study product infusion. A T2 image will also be obtained in all subjects to provide information about tissue edema, which in turn will provide information about whether ischemia has occurred over the past several days [to determine whether ischemia is in fact present which presumably would be on the basis small vessel disease]. A full 2D and Doppler transthoracic echocardiography with speckle tracking will be performed also prior to study product infusion.

Eligible subjects will receive either a stem cell or placebo infusion based on randomization at the two clinical sites as approved by the sponsor.

Follow-up visits will occur at days 30, 60 and 90. At 90 days the two groups will change arms and the placebo group will receive the stem cell infusion also and the initially treated group will receive a LRS at a volume of 1 mL/kg. All patients will be evaluated at 30, 60 and 90, days after this new infusion treatment. Information on adverse events, concomitant medications, vital signs, clinical laboratory tests and physical examination will be collected according to the schedule of assessments (Appendix A). All concomitant guideline based medical care will continue as prescribed by the subject's personal physician(s). Use of other investigational agents or treatments is not allowed during this study.

## STUDY ENDPOINTS

#### **PRIMARY ENDPOINT**

#### Safety

Baseline and days 30, 60, and 90 post-initial infusion. After the crossover phase all patients will be evaluated at days 30, 60, and 90 days post the new infusion

- 1. Procedural complications
- 2. Vital signs
  - a. Temperature
  - b. Systolic blood pressure/diastolic blood pressure
  - c. Heart rate
  - d. Respiratory rate
  - e. Weight
- 3. Changes in heart failure medications
- 4. Clinical arrhythmias, defibrillator firing and anti-tachycardia pacing
- 5. Laboratory tests
  - a. CBC/PLT/differential
  - b. Chemistry-12, including liver function tests
  - c. Creatinine kinase
  - d. Troponin-I
- 6. Electrocardiogram
- 7. Composite of all-cause mortality all-cause admission and need for co-intervention. E.g. IV diuretics for worsening heart failure (RADIENCE trial criteria).

#### Baseline and day 90 post stem cell infusion

Pulmonary function test

## SECONDARY ENDPOINT

#### Efficacy

Change in LVEF from baseline to day 90 post initial infusion. After the crossover phase all patients will be evaluated for change from the new baseline (day 90 after the initial phase) to day 90 post new infusion.

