## 2.7 Clinical Experience with Stemedica itMSCs

Two clinical studies are currently ongoing using cells prepared at Stemedica's cGMP manufacturing facility. The first study targets ischemic stroke and is being conducted at the University of California, San Diego (UCSD), and at Mercy Gilbert Medical Center in Gilbert, Arizona using Stemedica's specially formulated ischemic adult allogeneic mesenchymal stem cells under US IND 14328. Stemedica completed the Phase I enrollment and treatment of 15 patients. All safety data were provided to DSMB for review. Only one mild event was possibly related to the study product. There were no clinically significant abnormalities reported on any post-administration scans or on post-administration physical examinations. In the second study "Intravenous Administration of Ischemic Tolerant Allogeneic Mesenchymal Stem Cells for Acute Coronary Syndrome Patients," Stemedica Cell Technologies, Inc. provided cGMP allogeneic itMSCs to the National Scientific Medical Center (NSMC) in Astana, Kazakhstan to conduct a clinical study in patients with STEMI, Principal Investigators: Professors [name], MD, PhD and [name], PhD . itMSCs were provided under 21 CFR §312.110 (4)(b) regulations and the study was conducted in compliance with the ICH-E6 (Good Clinical Practice) guidelines and all subjects provided signed informed consent. Nineteen subjects in the itMSC group received intravenously. There were no deaths and no SAEs reported to be related to the study drug. In 19 itMSC treated and 15 open control patients, i.v. injection of 45-50 million cells 7 days after stenting for STEMI was administered without any SAEs reported. LVEF improved significantly from 42.1% to 52.3% and 54.7% after 3 and 6 months, respectively. In contrast there was no improvement in LVEF in the control group; LVEF 42.3%, 42.8% and 46.1%, at baseline, 3 and 6 months respectively. Similar changes in end-systolic and end-diastolic volumes were noted. There was also an increase reported in circulating levels of growth factors (VEGF and FGF) in the itMSC treated group, and CRP and BNP levels were lower in the treated group compared to controls during follow-up.

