## 9 STATISTICAL CONSIDERATIONS

Statistical analyses will be descriptive. Summary statistics will consist of sample size (N), means, standard deviations, medians, and minimum and maximum values for continuous variables, and counts and percentages for categorical variables. Tables will summarize all safety and efficacy outcome measures by actual treatment received. Summary tables will indicate the number of subjects with complete data for each measurement, event or outcome. No substitutions will be made for missing data. All analyses will be based on available data.

A detailed Statistical Analysis Plan will be written prior to data analysis. Significant deviations from the original statistical analysis plan will be detailed in the final study report.

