#### 9.3 Efficacy Analyses

The actual score and calculated change from baseline for each outcome measure (LV end diastolic volume, LVEF, Ventricular Arrhythmias, Kansas City Cardiomyopathy Questionnaire and the New York Heart Association Classification) will be tabulated for each scheduled assessment visit. Summary statistics will consist of sample size (N), means, standard deviations, medians, and minimum and maximum values will be used to summarize the data. Subjects who receive complete dose of investigational product or LRS and have post-administration assessments will be used as the efficacy evaluable population for statistical analysis.

The primary efficacy endpoint will be evaluated and is the change from baseline to Day 90, and 180 on the above measures. For each of the efficacy endpoints, a mixed-effect repeated measures (MMRM) analysis will be conducted to determine if the change from baseline to six months in the experimental group is different than that for the placebo group. The model will include the change in endpoint score from baseline to each post-baseline visit as the outcome variable, the baseline score, time, study site, treatment group and time-by-treatment interaction as fixed effects, and participant as a random effect. An unstructured covariance matrix will be used to model the within-subject variance-covariance errors. Time (0, 30d, 90d, and 180d) will be treated as a categorical variable in the analysis. The mixed model seamlessly accommodates different times of measurement as well as missed measurement and data from participants who are lost to follow up.

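### Tabulating efficacy by treatment received counts second-phase follow-up after cells as LRS data, with no provision for carry-over, and this can bias the cells-versus-LRS LVEF tables

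*Combined protocol and SAP*

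**What the plan says.** The efficacy endpoint (Synopsis and Section 4.2, Secondary Endpoint) has two parts. The first is "Change in LVEF from baseline to day 90 post initial infusion". For the second, all patients are "evaluated for change from the new baseline (day 90 after the initial phase) to day 90 post new infusion". The exploratory measures restart their baseline at Day 90 in the same way.

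Section 7.3 makes the Day 90 visit the day of the crossover infusion. Section 9.1 gives LRS at that point to the group first given cells, and cells to the group first given LRS. No washout is stated.

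On presentation, Section 9 states: "Tables will summarize all safety and efficacy outcome measures by actual treatment received". It also states: "Statistical analyses will be descriptive". Section 9.3 tabulates, for each scheduled visit, the following: "The actual score and calculated change from baseline for each outcome measure". The mixed model in Section 9.3 has "the baseline score, time, study site, treatment group and time-by-treatment interaction as fixed effects, and participant as a random effect". The documents contain no carry-over term, no sequence-by-period layout and no rule that limits the cells-versus-LRS comparison to the initial phase.

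**The concern.** From Day 90 to Day 180 every subject on LRS is also a subject 90 to 180 days after cells. Followed literally, Section 9 puts those values under LRS. The change in that period is then the later course of the cell effect plus whatever LRS-treated patients would do anyway. It is not a placebo response.

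The secondary objective is the effect of cells on LV structure and function, and LVEF is the only secondary endpoint. Because the analyses are called descriptive, these tables would be a main efficacy result. A reader who compares the cells column with the LRS column would not know that the second-phase comparator had already been treated with cells.

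**Working it through.** The plan gives no effect size, SD or power for LVEF, so there is no planned figure to reproduce. The check is what each planned table would show on average.

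**Symbols.** T is the cell effect at 90 days. g is the further control-adjusted change in that effect from Day 90 to Day 180 in cells-first subjects (negative if it fades). p1 and p2 are the drifts common to both groups in the two phases. Effects are taken as additive and the sequences as equal in size.

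| Sequence | Change, Day 0 to 90 | Change, Day 90 to 180 |
|---|---|---|
| Cells first | p1 + T (cells) | p2 + g (LRS) |
| LRS first | p1 (LRS) | p2 + T (cells) |

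**Changes from the reset baseline, cells minus LRS**
- Initial phase: T
- Second phase: (p2 + T) − (p2 + g) = T − g
- Phases pooled: [(p1 + T) + (p2 + T)]/2 − [p1 + (p2 + g)]/2 = T − g/2

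**Actual scores, cells minus LRS** (equal mean score at Day 0)
- Day 90: T
- Day 180: (p1 + p2 + T) − (p1 + p2 + T + g) = −g
- Phases pooled: average of T and −g = (T − g)/2

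**Illustrative inputs, Section 2.7.** For the treated arm, "LVEF improved significantly from 42.1% to 52.3% and 54.7% after 3 and 6 months, respectively". Controls were 42.3, 42.8 and 46.1 at baseline, 3 and 6 months.
- T = (52.3 − 42.1) − (42.8 − 42.3) = 10.2 − 0.5 = 9.7
- g = (54.7 − 52.3) − (46.1 − 42.8) = 2.4 − 3.3 = −0.9
- Effect remaining at 6 months: 12.6 − 3.8 = 8.8

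That study enrolled STEMI patients with an open control group, so it does not establish T or g for non-ischemic heart failure. The other rows are assumed values of g, as fractions of T = 9.7.

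| Course after Day 90 | g | Change, pooled | Change, second phase | Score, pooled | Score, Day 180 |
|---|---|---|---|---|---|
| Section 2.7 figures | −0.9 | 10.15 | 10.6 | 5.3 | 0.9 |
| Flat | 0 | 9.7 | 9.7 | 4.85 | 0 |
| Half fading | −4.85 | 12.125 | 14.55 | 7.275 | 4.85 |
| Full fading | −9.7 | 14.55 | 19.4 | 9.7 | 9.7 |
| 25% further growth | 2.425 | 8.49 | 7.275 | 3.64 | −2.425 |

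The change table is right when the effect is flat, and the score table is right only when the effect has gone completely. No single course makes both right, so two planned tables of the same data would disagree.

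**Could the trial detect the problem?** The difference between sequences in total change from Day 0 to Day 180 has expectation g. With 10 per sequence its standard error is SD × √(2/10). At an assumed SD of 4, 6 or 8 points this is 1.79, 2.68 or 3.58. Power for g of 2.4 points (normal approximation, two-sided 5%) is 27%, 14% or 10%. Carry-over of that size would probably go unnoticed.

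**The case against.** Several arguments limit the point, and most of them stand.

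- **Bias is not certain.** With the reset baseline, an effect that simply persists cancels out. A reader might infer that the restarted baseline causes the trouble. On the Section 2.7 figures it helps: the pooled error is +0.45 (10.15 − 9.7), against −4.4 (5.3 − 9.7) if changes were taken from Day 0.
- **Section 2.7 does not show a growing effect.** The treated arm's rise of 2.4 points from 3 to 6 months invites that reading, but controls rose 3.3. Net of controls the effect slips from 9.7 to 8.8. Full fading, with its 50% overstatement (14.55 against 9.7), is an assumed extreme, and most of the effect in that study remained at 6 months.
- **Pooling is only one reading.** No section says that the two phases will be combined in one column. The endpoint defines two separate changes, Section 9.3 tabulates by visit, and treatment received may simply mean as treated rather than as randomised. Tables by visit leave a clean Day 90 comparison.
- **Durability is not wholly hidden.** A maintained gain shows as zero change in the second phase, but Section 9.3 also reports actual scores by visit.
- **This is an exploratory safety study,** and Section 9 promises a detailed analysis plan in which table layout could be settled.

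These points reduce the size and certainty of the bias but do not remove the mislabelling. Even without pooling, the second-phase LRS column consists wholly of subjects already given cells. The score tables that show durability are the ones with no protection by treatment received: about 0.9 at Day 180 against a 90-day effect of 9.7.

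**Conclusion.** The point holds as a risk of bias, not as a demonstrated bias. As written, the plan counts follow-up after cells as LRS data in the second phase and provides nothing to detect or remove carry-over.

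For reset-baseline changes the distortion is zero if the effect is flat after Day 90 and about half a point pooled on the Section 2.7 figures. Over the assumed range from full fading to 25% further growth, the pooled result runs from 14.55 to 8.49 against 9.7. For actual scores it is large unless the effect has largely gone: 5.3 pooled and 0.9 at Day 180 on the same figures.

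These sizes assume additive effects, equal sequences, and a STEMI study standing in for this population. The 10 per sequence comes from the Synopsis and Section 4.1. Sections 5.2 and 6.1 give other group sizes, which must be reconciled; unequal sequences would also stop the common drift from cancelling in the pooled figures.

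The mixed-model test in Section 9.3, meant to "determine if the change from baseline to six months in the experimental group is different than that for the placebo group", compares groups that have both had cells by then. That is a separate issue, and correcting it would not correct the tables. Severity: should be fixed before analysis, not critical, because LVEF is secondary and the study is descriptive.

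**What to change.** Amend the Secondary Endpoint text (Synopsis and Section 4.2), Section 9 and Section 9.3, and carry the changes into the detailed analysis plan:

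1. Name the initial-phase change in LVEF, baseline to Day 90 by randomised group, as the main cells-versus-LRS contrast.
2. Tabulate actual scores and changes by sequence and period (four cells), not by treatment received alone. Apply the same layout to the other efficacy measures.
3. Label Day 90 to 180 in the cells-first group as follow-up after cells. Show it against the original baseline as well as Day 90, and do not count it as LRS or placebo data.
4. Report Day 90 to 180 in the LRS-first group as a within-subject before-after result.

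The cost is endpoint and table wording, with no new data. With 10 per group, the LRS comparator falls from about 20 subject-periods to about 10, so it is less precise. The periods given up are not clean placebo data, and they remain in the report under their own label.

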#### **EXPLORATORY ENDPOINTS**

Changes between baseline and days 90 post-initial infusion. After the crossover phase all patients will be evaluated for changes from the new baseline (day 90 after the initial phase) to day 90 post new infusion. MRI

- 1. Left ventricular end systolic volume index
- 2. Wall motion segmental score
- 3. LV end-systolic and end-diastolic dimensions
- 4. T2 MRI imaging for tissue edema (an index of recent ischemia)

Changes between baseline and days 90 post initial infusion. After the crossover phase all patients will be evaluated for changes from the new baseline (day 90 after the initial phase) to day 90 post new infusion. Echocardiogram

- 1. Changes in LV mechanics by speckle-tracking echocardiography (longitudinal and circumferential strain and strain rate)
- 2. Estimated systolic pulmonary artery pressures
- 3. Changes in MR severity (most patients have mild to moderate MR)

Changes between baseline and days 30, 60, and 90 post-initial infusion. After the crossover phase all patients will be evaluated for changes from the new baseline (day 90 after the initial phase) to day 30 and 90 post new infusion

#### Exercise capacity

6 minute walk distance

Health status

- a. New York Heart Association Class (NYHA) class
- b. Kansas City Cardiomyopathy Questionnaire

Heart failure status

Clinical Congestion Score

Biomarkers

- 1. Brain natriuretic peptide, troponin
- 2. Growth factors (FGF, VEGF)

## SUBJECT SELECTION

Subjects will be selected using the following inclusion and exclusion criteria:

## **INCLUSION CRITERIA**

- 1. Males and females ≥18 years of age
- 2. LVEF ≤35% on echocardiogram within 6 months of randomization to undergo MRI
- 3. Screening cardiac MRI at baseline with
  - a. Ejection fraction ≤40%
  - b. No evidence of hyper-enhancement
- 4. Absent or non-obstructive coronary artery disease on x-ray angiography or coronary computed tomography within the past 3 years
- 5. On standard therapy medical therapy (at the discretion of the investigator) including ACE-inhibitors, beta-blockers, and mineralocorticoid receptor antagonists, as tolerated, for at least 3 months
- 6. NYHA class II-III symptoms
- 7. Ability to understand and provide signed informed consent
- 8. Reasonable expectation that patient will receive standard post-treatment care and attend all scheduled safety follow-up visits

## **KEY EXCLUSION CRITERIA**

- 1. Pregnant or nursing women or those of childbearing age and not using an effective method of contraception
- 2. History of stroke within 3 months
- 3. Cardiac surgery within 3 months prior to randomization or the likelihood of a requirement for such procedures during the study period
- 4. Current ICD or CRT or implantation planned with 6 months of infusion
- 5. Presence of clinically significant, uncorrected valvular heart disease, hypertrophic or restrictive cardiomyopathy, active myocarditis, or uncontrolled hypertension
- 6. History of cardiac arrest or life-threatening arrhythmias within 3 months
- 7. Treatment with parenteral inotropic agents within 1 month of randomization
- 8. Anticipated cardiac transplantation within 1 year
- 9. Illness other than heart failure with life expectancy less than 1 year
- 10. Received an experimental drug or device within 30 days of randomization
- 11. Left ventricular assist device or implantation planned in the next 6 months
- 12. Patients with complex congenital heart disease
- 13. Uncontrolled seizure disorder
- 14. Presence of immune deficiency
- 15. Clinically significant hematologic, hepatic, or renal impairment as determined by screening clinical laboratory tests
- 16. Presence of any other clinically-significant medical condition, psychiatric condition, or laboratory abnormality, that in the judgment of the investigator or sponsor for which participation in the study would pose a safety risk to the subject
- 17. Inability to comply with the conditions of the protocol

- 18. Malignancy within the previous five years, except basal cell carcinoma, provided that it is neither infiltrating nor sclerosing, and carcinoma in situ of the cervix
- 19. Active myocarditis or early postpartum cardiomyopathy (within six months).
- 20. Systemic corticosteroids, cytostatics, immunosuppressive drug therapy (cyclophosphamide, methotrexate, cyclosporine, azathioprine, etc.), and DNA depleting or cytotoxic drugs taken within four weeks prior to study treatment
- 21. Porphyria
- 22. Allergy to sodium citrate or any "caine" type of local anesthetic
- 23. Any contraindication for gadolinium use for MRI
- 24. Patient scheduled for hospice care
- 25. Clinically relevant abnormal findings in the clinical history, physical examination, ECG, or laboratory tests at the screening assessment that would interfere with the objectives of the study or would preclude safe completion of the study. Abnormal findings could include: known HIV infection or other immunodeficiency state, chronic active viral infection (such as hepatitis B or C), acute systemic infections (defined as patients undergoing treatment with antibiotics), gastrointestinal tract bleeding, or any severe or acute concomitant illness or injury
- 26. Any other medical, social, or geographical factor that would make it unlikely that the patient could comply with study procedures (e.g., alcohol abuse, lack of permanent residence, severe depression, disorientation, distant location, or noncompliance)

